8. PRESTUDY AND CONCOMITANT THERAPY

Prestudy therapies administered up to 28 days before the first dose of study drug (Part A) or 28 days before randomization (Part B) must be recorded at screening. Prior systemic therapies for MDS or MPN administered before signing of the informed consent should be collected at screening. Concomitant therapies must be recorded throughout the study beginning with signing of the

Informed Consent Form and continuing until 30 days after the last dose of study drug. The sponsor must be notified in advance (or as soon as possible thereafter) of any instances in which prohibited therapies are administered.

Following Amendment 7 and when 270 deaths have occurred or 6 months after the last subject is enrolled (whichever occurs first), follow up of subjects and data collection will end. Subjects who are continuing to derive benefit from decitabine treatment as assessed by their investigator may continue to receive decitabine; during this period, only serious adverse events will be monitored and entered into the Company safety repository.

8.1. Permitted Medications and Supportive Therapies

All concomitant medications for medical conditions other than AML are permitted, as clinically indicated. All supportive therapies, other than anticancer treatment needed for the management of subjects enrolled in this study, are encouraged.

The following medications and supportive therapies are examples of support therapies that are recommended during the study:

- Short-term (<3 days) treatment with low doses of systemic corticosteroids when medically necessary for the control of acute symptoms or for premedication of talacotuzumab;
- Prophylactic antibacterial, antifungal, or antiviral agents need to be used per institutional guidelines;
- Growth factors are strongly recommended to be used for the treatment of febrile neutropenia (temperature $\geq 38.5^{\circ}\text{C}$ and absolute neutrophil count $< 1,000/\mu\text{L}$) or an active bacterial or fungal infection (ie, requiring intravenous anti-infectives or extensive supportive care) in neutropenic subjects. Growth factors need to also be used to prevent treatment delay due to neutropenia.
- Red blood cell and platelet transfusions per institutional guidelines.

8.2. Prohibited Therapies

The following medications are prohibited during the study:

- Concurrent systemic corticosteroids except for short-term treatment and mandatory premedication;
- Plasmapheresis, cytoreduction by hydroxyurea or other concurrent anticancer therapy. Of note: treatment with hydroxyurea and plasmapheresis has to be discontinued prior to start of study therapy;
- Any investigational agent; and
- Any live attenuated vaccination.

8.3. Subsequent Antineoplastic Therapies

Administration of any other antineoplastic therapy, for reasons other than treatment failure (defined in Section 9.2.1.1) or relapse from CR/CRi, is strongly discouraged until treatment

failure or relapse is established. After treatment failure or relapse is established, subsequent therapy is permitted at the investigator's discretion. Subsequent therapy (including start date, end date, and best response) should be documented in the appropriate section of the eCRF.

9. STUDY EVALUATIONS

Following Amendment 6, which incorporated the IDMC's recommendations to close enrollment to the study and discontinue talacotuzumab treatment for subjects receiving talacotuzumab + decitabine and offer to continue decitabine alone, all subjects will continue to be followed for survival and subsequent anti-cancer therapy. During the treatment phase with decitabine, subjects will be monitored for serious adverse events.

Following Amendment 7 and when 270 deaths have occurred or 6 months after the last subject is enrolled (whichever occurs first), follow up of subjects and data collection will end. Subjects who are continuing to derive benefit from decitabine treatment as assessed by their investigator may continue to receive decitabine; during this period, only serious adverse events will be monitored and entered into the Company safety repository.

9.1. Study Procedures

9.1.1. Overview

The [Time and Events Schedules: Tables 1A, 1B, 1C, 1D, 2A, and 2B](#) summarize the frequency and timing of efficacy, pharmacokinetic, immunogenicity, pharmacodynamic, biomarker, pharmacogenomic, patient-reported outcomes, and safety measurements applicable to this study. Every effort should be made to keep subjects on the study schedule as planned from Study Day 1. At each visit, study assessments should be completed before study drug administration. All PRO assessments should be conducted/completed before any tests, procedures, or other consultations to prevent influencing subject perceptions but prior to and on the day of the actual study drug administration.

Post-baseline disease evaluations may be conducted ± 7 days from the scheduled visit date, if necessary. At the following visit, the subject should return to the original planned schedule. Additional serum or urine pregnancy tests may be performed, as determined necessary by the investigator or required by local regulation, to establish the absence of pregnancy at any time during the subject's participation in the study.

Medical resource utilization data will be collected. Refer to Section [9.8](#) for details.

Assuming a study duration of 6 cycles, the total blood volume to be collected from each subject will be approximately 336 mLs for subjects participating in Part A, 541 mLs for subjects participating in Part B Arm 1 (decitabine + talacotuzumab) and 387 mLs for subjects participating in Part B Arm 2 (decitabine only). Repeat or unscheduled samples may be taken for safety reasons or for technical issues with the samples.

9.1.2. Screening Phase

The signed informed consent form (ICF) must be obtained before any study-specific procedures are performed. The Screening Phase begins when the first screening assessment is conducted (that was not performed as part of the subject's standard of care). During the Screening Phase, eligibility criteria will be reviewed and a complete clinical evaluation will be performed as specified in [Time and Events Schedule Tables 1A](#) and [1B](#). Screening procedures will be performed within 28 days before first dose (Part A) or within 28 days before randomization (Part B).

9.1.3. Open-Label Treatment Phase

Details of the procedures performed during the Treatment Phase are outlined in the [Time and Events Schedule Tables 1A](#), [1B](#), and [1C](#). For Part A, treatment will start on Day 1 with an IV infusion of talacotuzumab and proceed as described in [Section 6.1](#). Subjects will continue on study and receive open label talacotuzumab in combination with decitabine in Part A until treatment failure, relapse from CR/CRi, unacceptable toxicity, death or other reasons specified in [Section 10.2](#).

For Part B, treatment with study drug should start within 3 days after randomization and continue until treatment failure, relapse from CR/CRi, unacceptable toxicity, death, or other reasons specified in [Section 10.2](#).

All subjects in Part A and Part B will be closely monitored for adverse events, laboratory abnormalities, and disease status. Clinical evaluations and laboratory studies may be repeated more frequently, if clinically indicated. If treatment failure or relapse from CR/CRi occurs, then the subject will complete the End-of-Treatment Visit and enter the Follow-up Phase. Subjects randomized into the decitabine + talacotuzumab arm can discontinue 1 drug (decitabine or talacotuzumab); while continuing treatment with the other drug.

End of Treatment

All subjects should have an End-of-Treatment Visit, unless a subject withdraws consent for study participation or is lost to follow up. The End-of-Treatment Visit is to occur within 30 days (+/- 7 days) after the last dose of study drug. Every effort should be made to conduct the End-of-Treatment Visit before the subject starts subsequent treatment.

9.1.4. Follow-up Phase

The Follow-up Phase will begin once a subject has completed the End-of-Treatment Visit. Subjects who discontinue before treatment failure or relapse from CR/CRi must continue to have disease evaluations according to the [Time and Events Schedule Tables 1A](#), [1B](#), and [1C](#). Subjects with unresolved drug-related adverse events of Grade 3 or higher as well as ongoing drug-related serious adverse events (SAEs) will be followed until event resolution. After treatment failure or relapse is documented, only subsequent anticancer therapy, concomitant therapy to treat a continuing drug-related adverse events (AE) \geq Grade 3 or serious adverse event (SAE), survival status, and other malignancies will continue to be collected. If this information is obtained via telephone contact, then written documentation of the communication must be available for

review in the source documents. If the subject has died, then the date and cause of death will be collected and documented on the eCRF.

End of Study

The end of study data collection is defined as when 270 deaths have occurred or 6 months after the last subject is enrolled, whichever occurs first. At that time, follow up of subjects will end. Subjects who are continuing to derive benefit from decitabine treatment as assessed by their investigator may continue to receive decitabine; during this period, only serious adverse events will be monitored and entered into the Company safety repository as described under Amendment 7.

9.1.5. Disease Evaluation and Clinical Cutoff

Disease evaluations will be performed for each subject per the [Time and Events Schedule Tables 1A](#) and [1B](#) until treatment failure, relapse from CR/CRi, or until the study has reached the clinical cutoff for OS or EFS, whichever occurs first. If the study continues enrollment to 400 subjects then the clinical cut-off for the final analysis of OS is when 270 subjects have died. If study enrollment stops with approximately 120 subjects, the clinical cut-off for the final analysis of EFS is when 90 EFS events have occurred. Enrollment was terminated after Interim Analysis #2 and the study will end 6 months after the last subject was enrolled.

9.2. Efficacy

9.2.1. Evaluations

Disease assessments based on bone marrow evaluations, peripheral blood counts, and clinical presentation will be conducted per the [Time and Events Schedule Tables 1A](#), [1B](#), and [1C](#) at the local laboratory. Cytogenetics will be evaluated at the local site.

In Part B, bone marrow aspirates will be collected every 2 cycles. All treatment decisions will be based on local assessments. Additionally, slides will be sent to a central laboratory for analysis of the percentage of leukemic blast cells. A portion of the bone marrow aspirate specimen will also be sent in the appropriate medium for MRD status. Bone marrow biopsy material is not required, unless an aspirate sample cannot be obtained (dry tap).

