Bone marrow aspirate/biopsy	
A portion of each sample should be sent to the central lab for confirmation of disease status. A portion of the aspirate should be sent to the central lab for MRD and biomarker analysis at Screening, at suspected CR/CRi, then every disease assessment until relapse or EOT.
 
Blood samples at matching time points will be taken for biomarker evaluations (CD123 expression, genomic characterization, and immunophenotyping).
 
Molecular genetics and cytogenetics samples analyzed per the local standard of care at screening, at suspected CR/CRi and then every disease assessment until relapse or EOT
	X (A biopsy can be used for confirmation of disease if taken within 6 weeks of randomization, but a fresh aspirate is required for MRD and biomarker analysis.)	
 Every 2 Cycles starting at Cycle 2 (between Day 14 and 28) until treatment failure or relapse from CR/CRi or CCO At time of suspected CR /CRi At time of suspected treatment failure or relapse from CR/CRi 	X (unless done within 2 weeks)	
Imaging	Per local standard of care and as clinically indicated. Report the disease assessment for AML related abnormalities including all sites of extramedullary disease	X	To repeat as clinically indicated per local standards. If extramedullary disease at baseline, repeat imaging (using the same modality) at time of best response		
Disease evaluation	Disease evaluation should be done based on information available; hematology, clinical presentation and bone marrow assessments.		
 Every 2 Cycles starting at Cycle 2 (between Day 14 and 28) until treatment failure or relapse from CR/CRi or CCO At time of suspected CR /CRi At time of suspected treatment failure or relapse from CR/CRi 	X	
Survival, subsequent therapy, other malignancies					X

Procedure (Part B)	Notes	Screening Phase	Open-Label Treatment Phase		Follow-up Phase
		Within 28 days before randomization	Day 1 of each cycle (\pm 48 hours) unless otherwise indicated (each cycle = 28 days)	EOT	Every 3 months (\pm 7 days)
Pharmacokinetic, Pharmacodynamic, and Biomarker Assessments see TIME AND EVENTS SCHEDULE (PK AND BIOMARKERS) – TABLE 2B					

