9.2.1.1. Disease Status

Subjects will be assessed for disease status according to the “Response Criteria in AML”⁹ with a modification by the Sponsor for treatment failure ([Table 6](#)). The modification is necessary because the original criteria were intended for evaluation of standard induction therapy with 3 days of an anthracycline and 7 days of cytarabine (3+7) or therapies of comparable intensity.

If treatment failure is suspected due to clinical indications or increased peripheral blast counts, then a bone marrow sample must be obtained to confirm treatment failure as defined below. In the case of overt leukostasis, uncontrollable coagulopathy, or new extramedullary leukemia

requiring immediate action and a bone marrow sample cannot be obtained, the sponsor must be consulted to confirm treatment failure for the subject.

For this study, treatment failure is defined as >25% absolute increase in the bone marrow blast count from baseline to the present assessment (eg, from 20% to 46%) on bone marrow aspirate (or biopsy in case of dry tap).

Stable disease is defined as response that does not qualify for a complete or partial response and does not meet the criteria for treatment failure.

The sponsor must be notified before subjects discontinue study treatment. Before subjects discontinue the Treatment Phase due to treatment failure or relapse from CR/CRi, sites will document treatment failure or relapse as soon as possible and within 48 hours. The primary reason for discontinuation of study treatment is to be recorded in the eCRF. For all subjects, the Sponsor should be informed as soon as treatment failure or relapse from CR/CRi is confirmed. Discontinuation criteria for all subjects must be reviewed and confirmed by the Sponsor prior to discontinuation.

Based on investigator's disease assessments across all cycles of treatment, overall best response during the entire study will be derived by the Sponsor. For an overall best response of stable disease, disease stabilization must have lasted for at least 8 weeks.

Category	Definition
Complete response (CR) ¹	Bone marrow blasts <5%; absence of blasts with Auer rods; absence of extramedullary disease; absolute neutrophil count $>1.0 \times 10^9/L$ (1000/ μ L); platelet count $>100 \times 10^9/L$ (100 000/ μ L); independence of red cell transfusions

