5.9. Disease Status per Central Review and Investigator’s Assessment

Disease status (including response) based on central review by the IRC will be the primary source for all pertinent analyses. Analyses based on investigator’s assessment will also be performed. Any major discordance between the 2 assessments affecting interpretation of study outcomes may be investigated.

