6.7.2. Secondary and Exploratory Efficacy Endpoints

6.7.2.1. Event-Free Survival

Event-free survival (EFS) is defined as the time from randomization to treatment failure, relapse from CR or CRi, or death from any cause, whichever occurs first. Subjects who did not reach any of these events will be censored at the last tumor assessment.

EFS will be analyzed in the same fashion as that of overall survival.

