6.7.2.5. Duration of Response

Duration of response is defined for subjects who achieved a best response of CR or CRi as the time from achieving CR or CRi to relapse. Duration will be censored at the time of last tumor assessment for subjects who did not relapse. Duration of response will be summarized descriptively using the Kaplan-Meier method. Duration of response for best response of CR and best response of CR plus MRD-negative CRi are similarly defined and will be summarized, respectively.

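### Evaluations stop on the local call of failure or relapse, but EFS and duration of response are taken from central review, and no analysis isolates local calls that central review does not confirm

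*Protocol*

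**What the plan says.** **Who decides, and when evaluations end.** Protocol Section 9.2.1: "All treatment decisions will be based on local assessments". Sections 9.1.3 and 10.2 end treatment at failure or relapse. Section 9.1.5 runs disease evaluations "until treatment failure, relapse from CR/CRi, or until the study has reached the clinical cutoff for OS or EFS, whichever occurs first", and Time and Events Schedule Table 1B repeats this for the two-cycle marrow and disease evaluations: "until treatment failure or relapse from CR/CRi or CCO". Neither place says whose call counts, but Section 9.2.1.1 has the site document the failure or relapse, so in practice it is the local one. From then on Section 9.1.4 drops disease evaluations: "After treatment failure or relapse is documented, only subsequent anticancer therapy, concomitant therapy to treat a continuing drug-related adverse events" and a few other items are collected, survival status among them.

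**Checks before stopping.** Section 9.2.1.1: "Discontinuation criteria for all subjects must be reviewed and confirmed by the Sponsor prior to discontinuation". That is a sponsor check. Confirmation by the IRC is not required.

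**Which source is analysed.** SAP Section 5.9: "Disease status (including response) based on central review by the IRC will be the primary source for all pertinent analyses". The same section also plans investigator-based analyses and says that major discordance may be investigated.

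**Censoring.** SAP Section 6.7.2.1, on EFS, where death from any cause is an event: "Subjects who did not reach any of these events will be censored at the last tumor assessment". SAP Section 6.7.2.5, on duration of response, where only relapse is an event: "Duration will be censored at the time of last tumor assessment for subjects who did not relapse".

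**The concern.** The assessor who ends the evaluations is not the assessor who supplies the events. When the two disagree, the central reviewer loses the follow-up on which a later event could be seen, at a time when the site believes the subject is failing. Censoring at that point depends on prognosis, so it is informative.

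Some disagreement is foreseeable. Footnote 6 to the Protocol's response table says that marrow blasts of 5% to 10% need a repeat marrow to confirm relapse, and SAP Section 5.9 itself anticipates discordance. The issue comes from ordinary local/central disagreement throughout the trial. It is separate from the end of IRC review after the second interim analysis, which SAP Section 5.2 handles.

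At stake are the IRC-based medians of two secondary endpoints and, because the trial is open-label, the EFS hazard ratio if unconfirmed calls are more frequent in one arm.

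**Working it through.** **1. Apply the SAP rules to a local call that the IRC does not confirm at that visit.**

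| What happens next | Duration of response (relapse calls) | EFS |
|---|---|---|
| IRC event seen at the end-of-treatment (EOT) assessment | Event, slightly late | Event, slightly late |
| No IRC event by EOT; dies before cutoff | Censored at last assessment | Event at date of death |
| No IRC event by EOT; alive at cutoff | Censored at last assessment | Censored at last assessment |

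**2. Reproduce the plan's EFS figure.** Inputs from Protocol Section 11.3: HR 0.59, 90% CI (two-sided 0.10), 80% power, 1:1 allocation. Schoenfeld: 4 × (1.645 + 0.842)² / (ln 0.59)² = 88.8, so 89 events against 90 stated. Power with 90 events is 0.805. Expected events with 120 subjects, 15 months of accrual, 5 further months and medians of 4.0 and 6.8 months: 60 × 0.850 + 60 × 0.692 = 92.6. The design figures hold.

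**3. Duration of response.** Let d be the share of relapses that are unconfirmed and censored at the relapse, and take the hazard as constant. The observed hazard is (1 − d) times the true one, so the median is multiplied by 1/(1 − d).
- d = 10%: 1/0.90 = 1.11, up 11%
- d = 20%: 1/0.80 = 1.25, up 25%
- d = 30%: 1/0.70 = 1.43, up 43%

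**4. EFS, one arm with a true median of 4.0 months.** Simulation of 300,000 subjects per arm. The total hazard is ln 2/4 per month. Assumptions: half of first events are failure or relapse; the death hazard after failure is 0.087 or 0.173 per month (medians of about 8 and 4 months); follow-up is uniform over 6 to 26 months. An unconfirmed call becomes an event at death if that precedes cutoff; otherwise it is censored at the call.

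| Unconfirmed | Observed EFS median (months) |
|---|---|
| 0% | 4.0 |
| 10% | 4.2 |
| 20% | 4.4–4.5 |
| 30% | 4.6–4.7 |

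Between 59% and 79% of unconfirmed calls become later death events. With 10% unconfirmed in one arm, 25% in the other and no true difference, the HR is about 0.92 to 0.95. With equal rates it stays at about 1.00. If 70% of first events are failure or relapse, the 10% versus 25% case gives 0.90 to 0.93.

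**5. EFS under the planned effect (HR 0.59), 15 + 5 months.** Assumptions: 70% of first events are failure or relapse; median survival after failure is 4.0 (control) and 4.6 months (combination). These give OS medians of 7.9 and 11.6 months, close to the planned 8.0 and 11.4.

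| Unconfirmed (control / combination) | Events, SAP rule | Events if every call were censored | Medians, SAP rule | HR, SAP rule |
|---|---|---|---|---|
| 10% / 10% | 90.6 | 86.3 | 4.3 / 7.2 | 0.59 |
| 30% / 30% | 86.3 | 73.2 | 4.9 / 7.9 | 0.59 |
| 10% / 30% | 88.4 | 80.4 | 4.3 / 7.9 | 0.53 |
| 30% / 10% | 88.5 | 79.0 | 4.8 / 7.1 | 0.65 |

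About 71% (control) and 64% (combination) of unconfirmed calls become death events. Across post-failure medians of 4 to 9 months and a 50% or 70% failure share, the range is 43% to 72%.

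**The case against.** **The investigator-based analysis already covers this.** It counts these calls at their dates, and comparing it with the IRC result shows how far the choice of source moves the estimates. That mitigates in part. But it changes the source for every subject, so it does not isolate the unconfirmed calls, and no count of them by arm is planned.

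**The Protocol makes unconfirmed calls less likely.** Suspected failure must be confirmed by marrow, part of each marrow sample goes to the central laboratory, and the sponsor reviews discontinuations. At EOT the marrow is waived if one was done within 2 weeks, but the disease evaluation and the peripheral blast count are not, and blood blasts alone can establish relapse. All of this stands. It reduces the number affected, and it is why the point concerns calls still unconfirmed after EOT. None of it is IRC confirmation before evaluations stop.

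**The central review charter may deal with discordance.** It is not among the documents, so this cannot be excluded. The SAP's censoring rules, as written, contain no exception for it.

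**The size is assumed.** This is correct. If the IRC is right and the local call is a false alarm, the IRC-based medians are not too long by these amounts.

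**Stronger readings that a reader might infer.** One is that every unconfirmed call is censored in EFS just as the subject fails. The documents do not support that: death is an EFS event and survival is still followed. Another is a spurious between-arm hazard ratio for duration of response (0.75/0.90 = 0.83 for 10% versus 25%). SAP Section 6.7.2.5 is descriptive, so no planned comparison would produce that figure.

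**Conclusion.** The point holds in limited form. For duration of response, a local relapse that the IRC does not confirm by EOT is censored at the last assessment, and this censoring is informative. For EFS the usual effect is to move the event to a later death; censoring applies only to subjects alive at cutoff.

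With an assumed 10% to 30% unconfirmed, the duration-of-response median is about 11% to 43% too long, and an EFS median of 4.0 months reads as about 4.2 to 4.7. The EFS hazard ratio is almost unchanged if discordance is equal between arms, and is about 0.92 to 0.95 for 10% versus 25% with no true effect. These sizes rest on three assumptions that the documents do not supply: the discordance rate, the share of EFS events that are failure or relapse together with survival after them, and the premise that every unconfirmed call is a true event that EOT does not pick up.

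The reach is modest. Both endpoints are secondary with no alpha allocated. The CR and OS analyses do not use these rules, and the decision to stop talacotuzumab, taken after OS met the futility criterion and CR missed significance, does not depend on them. The change is still worth making, because no planned analysis shows whether the IRC-based results depend on unconfirmed calls.

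**What to change.** In SAP Sections 6.7.2.1 and 6.7.2.5, add one sensitivity analysis of the IRC-based result. Where disease evaluations ended because of an investigator-assessed treatment failure or relapse (relapse only, for duration of response) and there is no IRC event at or before that date, count the investigator's event at its date. Report the number of such subjects by arm beside the IRC-based and investigator-based results.

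The cost is a paragraph of SAP text and one additional program run on data already collected. It needs no new visits or samples and no change to clinical conduct. The downside is that the analysis mixes two sources and brings in open-label local calls, so it should be labelled supportive only.
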